## 3 Study Design

---

This will be a double-masked, randomized, bilateral, two-week crossover, dispensing study, comparing the Orion Test lens against Gemini Control lens, such that each daily replacement lens type will be worn on a daily wear, single use basis for two weeks each. Each subject will be randomized to wear either the Test lenses or the Control lenses potentially as an unmatched pair (with regards to power), according to a predetermined randomization schedule. All lenses will be

replaced daily. Electronic (e.g. email or SMS text survey link) comfort questionnaires will be administered during the course of the study.

It is anticipated that this study will involve up to 4 scheduled visits:

- Visit 1a: Enrollment / Screening / Baseline Visit (Day 0)
- Visit 1b: Dispensing of Pair 1 (Day 0)
- Visit 2: Two-week follow-up of Pair 1 (-1/+4 days) and Dispensing of Pair 2
- Visit 3: Two-week follow-up of Pair 2 (-1/+4 days) and Exit

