### **3.1 Study Design & Comparator Justification**

---

The study design was chosen since the influence of confounding covariates is reduced in crossover designs, as each subject acts as his or her own control. Crossover study designs are also statistically more efficient.

The choice of comparator was made since the aim of the project is to match the clinical performance of the Gemini (Acquiane) lens, which is CE-marked / already approved in Europe.

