#### Inclusion criteria

A person is eligible for inclusion in the study if he/she:

- Is at least 18 years of age and has full legal capacity to volunteer.
- Is no greater than 55 years of age.
- Has read and understood the information consent letter.
- Is willing and able to follow instructions and maintain the appointment schedule.
- Is an adapted soft contact lens wearer having worn lenses for a minimum of 4 weeks prior to the study.
- Has spectacle cylinder  $\leq 1.00D$  in both eyes.
- Has spherical contact lens power requirement between  $-1.00D$  and  $-6.00D$  in both eyes.
- Has manifest refraction visual acuities (VA) equal to or better than logMAR equivalent of 20/20 in each eye.
- Wears CLs in both eyes (monovision acceptable, but not monofit)
- Has clear corneas and no active ocular disease.
- Has not worn lenses for at least 12 hours before the examination.
- Is willing to wear the study contact lenses for a minimum 8 hours per day/6 days per week

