### 7.3.2 Visit 1b: Dispensing Visit (Pair 1)

*Dispensing visit may occur on same day as Visit 1a. If Visit 1b is conducted on a different day to Visit 1a, slit lamp biomicroscopy should be conducted again to confirm eligibility.*

- HVID (mm) and palpebral aperture size (mm) measurements using slit lamp oculars.
- The first study pair of contact lenses will be selected by the investigator according to the randomization table [REDACTED] insertion by the subjects. Subjects will be dispensed the lens power nearest to their refractive error requirement.
- Lenses should be allowed to settle for 10 minutes.
- An initial fit assessment will be made to ensure lens fit is acceptable (Y/N). The subject should be discontinued and exited if the lens fit is found unacceptable and the primary reason for poor fit recorded on the CRF and video footage of the fit collected.
- Monocular spherical over-refraction (SOR) will be conducted to determine if a different lens power is required.
- Monocular and binocular **HIHC** and **HILC** distance logMAR visual acuities will be recorded (SOR will be used if the subject is wearing monovision).
- Final lenses will be inserted and allowed to settle for a further 10 minutes, if applicable.

- [REDACTED]

- [REDACTED]
- [REDACTED]
- [REDACTED]
- [REDACTED]
- [REDACTED]
- [REDACTED]
- [REDACTED]
- [REDACTED]
- [REDACTED]

- Lens surface will then be assessed and graded after settling per guidelines detailed in the CVI grading scales ( [REDACTED] )
  - [REDACTED]
  - Wettability (0-4 scale)
  - [REDACTED]
  - [REDACTED]
- Lens fit will then be assessed and graded according to the guidelines detailed in CVI Grading scales ( [REDACTED] ).
  - Lens centration (0.1mm steps)
  - [REDACTED]
  - Post-blink movement (0.1mm steps)
  - Mobility rating (0.50 steps)
  - Overall lens movement (-2 to +2 scale)
  - Overall lens fit acceptance and investigator reason, if unacceptable (0.25 steps). Video will be recorded in the event of poor fit. Video will be recorded in the event of poor fit.
- The subject will be instructed to wear the study lenses for a minimum of 8 hours per day / 6 days per week.
- The subject will be dispensed adequate lenses (including spares) to last them until the next study visit.
- The subject will be discharged and scheduled to return for Visit 2 within the required study visit window.

### 7.3.3 Visit 2: Two-Week Follow-up Pair 1 (-1/+4 days) & Dispensing Pair 2

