*Subjects will be asked to wear lenses for **at least 3 hours** prior to the visit appointment.*

- Subjective responses will be collected per the Final Questionnaire [REDACTED] including:
  - Overall satisfaction (7-point Likert scale)
  - Comfort satisfaction & comfort rating (7-point Likert & 100-point scales)
  - [REDACTED]
  - [REDACTED]
  - [REDACTED]
  - [REDACTED]
  - [REDACTED]
  - [REDACTED]
  - [REDACTED]

- [REDACTED]
  - Lens handling (7-point Likert & 100-point scales)
  - [REDACTED]
  - [REDACTED]
  - Lens holding/handling (5-point Likert scales)
  - Vision (7-point Likert & 100-point scales)
- The following information will be collected from the subject by the investigator:
    - Wear time at visit (hours).
    - Average time of insertion and removal during previous week, i.e. average time (hours).
    - Maximum wear time during previous week (hours).
    - Average time of day lenses become uncomfortable, if at all, i.e. average comfortable wear time (hours).
    - Use and frequency of comfort / re-wetting drops during past week (if any).
  - Monocular and binocular **HIHC** and **HILC** distance logMAR visual acuities will be recorded (a spherical over-refraction will be performed for the distance eye and recorded first if the subject is wearing monovision).
  - Lens surface will then be assessed and graded per guidelines detailed in the CVI grading scales [REDACTED]
    - [REDACTED]
    - Wettability (0-4 scale)
    - [REDACTED]
    - [REDACTED]
  - Lens fit will then be assessed and graded according to the guidelines detailed in CVI Grading scales [REDACTED]
    - Lens centration (0.1mm steps)
    - [REDACTED]
    - Post-blink movement (0.1mm steps)
    - Mobility rating (0.50 steps)
    - Overall lens movement (-2 to +2 scale)
    - Overall lens fit acceptance and investigator reason, if unacceptable (0.25 steps). Video will be recorded in the event of poor fit.
  - The lenses will be removed and stored in either an unbuffered or phosphate buffered (not borate) saline for return to the Sponsor.

- Slit lamp biomicroscopy will be assessed according to the CVI approved study biomicroscopy CRF [REDACTED]

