### Dispensing Visit (Pair 2)

- The subject will undergo a saline washout.
- The second study pair of contact lenses will be selected by the investigator according to the randomization table [REDACTED] for insertion by the subjects. Subjects will be dispensed the lens power nearest to their refractive error requirement.
- Lenses should be allowed to settle for 10 minutes.
- An initial fit assessment will be made to ensure lens fit is acceptable (Y/N). The subject should be discontinued and exited if the lens fit is found unacceptable and the primary reason for poor fit recorded on the CRF and video footage of the fit collected.
- Monocular spherical over-refraction (SOR) will be conducted to determine if a different lens power is required.
- Monocular and binocular **HIHC** and **HILC** distance logMAR visual acuities will be recorded (SOR will be used if the subject is wearing monovision).
- Final lenses will be inserted and allowed to settle for a further 10 minutes, if applicable.
- Subjective responses will be collected per the Post-Settling Questionnaire [REDACTED], including:
  - [REDACTED]
  - [REDACTED]
  - [REDACTED]
  - [REDACTED]
  - [REDACTED]
  - [REDACTED]
  - [REDACTED]
  - [REDACTED]
  - Lens movement/awareness (5-point Likert scales)
  - Vision (7-point Likert & 100-point scales)
- Lens surface will then be assessed and graded after settling per guidelines detailed in the CVI grading scales [REDACTED]
  - [REDACTED]
  - Wettability (0-4 scale)
  - [REDACTED]
  - [REDACTED]

- Lens fit will then be assessed and graded according to the guidelines detailed in CVI Grading scales ( [REDACTED] ).
  - Lens centration (0.1mm steps)
  - [REDACTED]
  - Post-blink movement (0.1mm steps)
  - Mobility rating (0.50 steps)
  - Overall lens movement (-2 to +2 scale)
  - Overall lens fit acceptance and investigator reason, if unacceptable (0.25 steps).  
Video will be recorded in the event of poor fit.
- The subject will be instructed to wear the study lenses for a minimum of 8 hours per day / 6 days per week.
- The subject will be dispensed adequate lenses (including spares) to last them until the next study visit.
- The subject will be discharged and scheduled to return for Visit 3 within the required study visit window.

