#### 7.3.4 Visit 3: Two-Week Follow-up on Pair 2 (-1/+4 days) & Exit

*Subjects will be asked to wear lenses for at least 3 hours prior to the visit appointment.*

- Subjective response will be collected per the Final Questionnaire [REDACTED] including:
  - Overall satisfaction (7-point Likert scale)
  - Comfort satisfaction & comfort rating (7-point Likert & 100-point scales)
  - Comfort on insertion (7-point Likert & 100-point scales)
  - Comfort at end of day (7-point Likert & 100-point scales)
  - [REDACTED]
  - [REDACTED] s)
  - [REDACTED]
  - [REDACTED]
  - [REDACTED]
  - Lens handling (7-point Likert & 100-point scales)
  - [REDACTED]
  - [REDACTED]
  - Lens holding/handling (5-point Likert scales)
  - Vision (7-point Likert & 100-point scales)
- The following information will be collected from the subject by the investigator:

[figure not shown]

- Wear time at visit (hours).
  - Average time of insertion and removal during previous week, i.e. average time (hours).
  - Maximum wear time during previous week (hours).
  - Average time of day lenses become uncomfortable, if at all, i.e. average comfortable wear time (hours).
  - Use and frequency of comfort / re-wetting drops during past week (if any).
- Monocular and binocular **HIHC** and **HILC** distance logMAR visual acuities will be recorded (a spherical over-refraction will be performed for the distance eye and recorded first if the subject is wearing monovision).
  - Lens surface will then be assessed and graded after settling per guidelines detailed in the CVI grading scales (Appendix 4).
    - [REDACTED]
    - Wettability (0-4 scale)
    - [REDACTED]
    - [REDACTED]
  - Lens fit will then be assessed and graded according to the guidelines detailed in CVI Grading scales [REDACTED]
    - Lens centration (0.1mm steps)
    - Corneal coverage (Yes / No / Borderline)
    - [REDACTED]
    - Mobility rating (0.50 steps)
    - Overall lens movement (-2 to +2 scale)
    - Overall lens fit acceptance and investigator reason, if unacceptable (0.25 steps). Video will be recorded in the event of poor fit.
  - The lenses will be removed and stored in either an unbuffered or phosphate buffered (not borate) saline for return to the Sponsor.
  - Slit lamp biomicroscopy will be assessed according to the CVI approved study biomicroscopy CRF [REDACTED]
  - Subjective response will be collected per the Lens Preference Questionnaire [REDACTED]

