## 10.2 Statistical analysis

---

Summary statistics will be produced (e.g. mean, standard deviation). Paired t-test will be used to compare slit lamp biomicroscopy, lens fit and subjective scores between study lens types. Repeated Measures Analysis of Variance (ANOVA) or paired analysis will be used to compare the variables between study visits. The critical alpha level for statistical significance will be set at  $p \leq 0.05$ , with adjustment for multiple comparisons.

All participants who were evaluated will be used in the analysis. In the event of missing data, individual data points will be excluded in the analysis and not extrapolated from the collected data.

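### The lens comparison in Section 10.2 is a plain paired t-test with no period term, although this is a two-period crossover whose two dispensing sessions differ by design

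*Combined protocol and SAP*

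**What the plan says.** Section 3 describes a double-masked crossover with two weeks on each lens: "Each subject will be randomized to wear either the Test lenses or the Control lenses", following a predetermined schedule. Section 3.1 defends the design partly on precision: "Crossover study designs are also statistically more efficient".

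Section 10.2 gives the lens comparison: "Paired t-test will be used to compare slit lamp biomicroscopy, lens fit and subjective scores between study lens types". The next sentence offers repeated measures ANOVA or a paired analysis, but for comparing variables between visits. It does not adjust the lens difference for period. No period, sequence, order or carryover term appears in the readable text.

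The visit procedures set the eye's condition before each assessment:

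- **Pair 1 dispensing.** The inclusion criteria in Section 7.1 require that the subject "Has not worn lenses for at least 12 hours before the examination", and Section 7.3.2 adds "Dispensing visit may occur on same day as Visit 1a".
- **Pair 2 dispensing.** Section 7.3.3 asks for at least 3 hours of Pair 1 wear before Visit 2. At that visit the lenses come out, the slit lamp examination follows, and then "The subject will undergo a saline washout" before Pair 2 goes in.
- **Two-week follow-ups.** The wear rule is the same for both pairs. Section 7.3.4 puts it as "Subjects will be asked to wear lenses for at least 3 hours prior to the visit appointment".

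Table 2 schedules lens fit and subjective assessments at both dispensing sessions.

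**The concern.** In a two-period crossover, each subject's Test-minus-Control difference contains the lens effect plus or minus the period effect, with the sign set by the order of wear. A paired t-test ignores this, with two consequences.

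1. The spread between orders is counted as random error, so the interval is wider than it need be even when orders are balanced.
2. If the analysed orders are unequal, part of the period effect is attributed to the lens.

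A period effect is most plausible on dispensing days, when rested eyes receive Pair 1 and eyes already worn in that day receive Pair 2. At the two-week visits a period effect is possible, but the schedule does not build one in. Slit lamp grading of the study lenses happens only at those visits, so the built-in asymmetry does not reach it.

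Nothing in the readable text keeps the analysed orders equal. Up to 70 subjects are dispensed for about 60 completers (Section 7.1), subjects with unacceptable fit exit at either dispensing, and missing points are dropped individually (Section 10.2). What is at stake is some of the efficiency claimed in Section 3.1, and a possible chance shift in the lens difference.

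**Working it through.** **Inputs from the documents.** Comfort margin 0.75, SD 1.3, 80% power, alpha 0.05, 53 completers (Section 10.1, Table 4); about 60 completers planned. Comfort is the only subjective score with a stated SD and margin. Its scale and timing are not given, so it serves as an illustration.

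**Inputs assumed.** Period effect P (period 2 minus period 1) of 0.25, 0.5 or 1.0 comfort unit. The last exceeds the margin and is an upper bound. Completers by order range from 30/30 to 35/25, because the allocation in Appendix 2 is not visible.

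**The plan's own figure.** Take 1.3 as the SD of one score, so the SD of the difference is 1.3 × √2 = 1.84. With a true difference of zero:

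- Two one-sided tests at 0.05 with 80% power give 53. One-sided 0.05 with 90% power also gives 53.
- Non-inferiority at the labelled 80% power gives 50 (one-sided 0.025) or 39 (one-sided 0.05).
- If 1.3 is already the SD of the difference, the last two become 26 and 20.

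I use SD 1.84 and one-sided 0.025, which corresponds to a two-sided 95% interval, and give milder readings below.

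**Formulas.** Let n1 subjects wear Test first and n2 Control first, n = n1 + n2, δ the true lens difference and sd the SD of the difference.

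- Mean paired difference by order: δ − P (Test first), δ + P (Control first).
- Bias of the overall mean: −P(n1 − n2)/n.
- Variance the paired t-test estimates: about sd² + P²[1 − ((n1 − n2)/n)²].
- Period-adjusted estimate: the average of the two order means, SE = ½·sd·√(1/n1 + 1/n2), n − 2 degrees of freedom.

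**Interval width at 30/30**, ratio √(1 + (P/sd)²):

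- Scale-free: √(1 + 0.25²) = 1.031 and √(1 + 0.5²) = 1.118.
- Comfort example: 1.009, 1.036 and 1.138 for P = 0.25, 0.5 and 1.0.

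**Bias at 35/25.** (35 − 25)/60 = 1/6 of P, so 0.04, 0.08 and 0.17.

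**Non-inferiority power and error**, 60 completers, margin 0.75, sd 1.84, one-sided 0.025. The estimated mean keeps variance sd²/n; the variance estimate follows a noncentral chi-square.

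| Quantity, unadjusted test | P = 0.25 | P = 0.5 | P = 1.0 | Period-adjusted |
|---|---|---|---|---|
| Power, 30/30 | 0.87 | 0.86 | 0.81 | 0.87 |
| Power, 32/28, bias against Test | 0.86 | 0.83 | 0.72 | 0.87 |
| Power, 35/25, bias against Test | 0.83 | 0.77 | 0.58 | 0.87 |
| Error at margin, 35/25, bias favours Test | 0.036 | 0.046 | 0.063 | 0.025 |

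**Milder readings at 30/30.** Unadjusted power is 0.93 / 0.92 / 0.89 at one-sided 0.05. It is 0.99 / 0.99 / 0.97 if 1.3 is already the SD of the difference (one-sided 0.025).

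**Cost if there is no period effect.** Degrees of freedom go from 59 to 58. The SE is unchanged at 30/30. At 35/25 it is ½·√(1/35 + 1/25)·√60 = 1.014 times as large. There the adjusted estimate has the lower mean squared error once P exceeds 6·√[sd²/4·(1/35 + 1/25) − sd²/60] = 0.24 unit, or 0.13 SD.

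**The case against.** The strongest reply is that the loss is small and the large figures are unlikely.

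- **Balance.** At equal orders the paired t-test is unbiased and conservative, and comfort power stays at 0.81 or more for every period effect tried. This stands.
- **Likelihood of 35/25.** If 70 are dispensed 35/35 and ten drop out at random, 35/25 needs all ten from one order, with probability about 0.0009; 32/28 or closer has probability 0.92. Under simple unblocked randomisation of 60 completers, 35/25 or worse has probability about 0.25. The schedule is not visible, so 35/25 marks the far end of the range and 32/28 is the fairer guide if allocation is blocked.
- **Illustration.** The visible comfort items belong to the two-week questionnaire, where no period effect is built in, and Section 10.2 names no non-inferiority test. Only the scale-free 3% and 12% apply directly to dispensing-day measures. This also stands.
- **Visit comparison.** The ANOVA sentence may reveal differences between visits, but it leaves the lens difference unadjusted.
- **Carryover.** A period term removes only a shift common to both orders. If Pair 1 affects Pair 2 dispensing scores differently by lens type, that effect remains.

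These points limit the size of the problem. None of them is a reason to keep the unadjusted test.

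**Conclusion.** The concern holds as a nearly free improvement of low-to-moderate importance; the change should be made. The period term is absent, and the protocol itself makes the dispensing sessions differ when Visits 1a and 1b share a day. With equal orders the cost is precision: a 3% or 12% wider interval at a period effect of 0.25 or 0.5 SD. With unequal orders there is also bias of (n1 − n2)/n times the period effect. Power of 0.58 or one-sided error of 0.063 requires both a 35/25 split and a period effect larger than the comfort margin, so these are outer bounds.

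The conclusion rests on an assumed period effect, an unseen allocation schedule and, for the comfort figures, an SD of the difference of 1.84. That the issue matters mainly on dispensing days is inferred from the schedule. The acuity conclusion is not threatened.

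**What to change.** In Section 10.2, replace the paired t-test for continuous lens comparisons with a linear mixed model: fixed effects for lens, period and sequence, and a random subject effect. For completers, the period-adjusted two-sequence t-test is equivalent. Report the lens difference with its 95% confidence interval. Under the mixed model, subjects with only one period also contribute. For measures taken on each eye, keep the subject as the unit by averaging the eyes or adding an eye-within-subject term. State that the period term does not remove carryover that differs by lens.

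The cost is SAP wording and one degree of freedom. Order and visit are already recorded, so no data collection or sample size change follows. The change should be made before unmasking.

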## 2 Study Objective

---

This is a feasibility study to evaluate the clinical performance of a new silicone hydrogel formulation lens (Orion) in comparison with Gemini A ██████ over a period of two weeks of wear.

The primary variables of interest are:

- Vision

The secondary variables of interest are:

- Comfort/comfort preference
- Surface wettability performance
- Lens fit
- Lens handling
- Anterior ocular health

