### 2.1 Study Hypothesis

---

The primary hypothesis is that there will be no difference in vision performance between the Orion Test lens and the Gemini Control lens.

The secondary hypothesis is that there will be no difference in performance between the Orion Test lens and the Gemini Control lens for any of the secondary variables.

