### 7.1 Participants

---

Up to 70 subjects will be enrolled and dispensed in order for approximately 60 subjects to complete the study. Each subject will be given a unique ID number. ID numbers will not be reused in event of screen failure or discontinuation. Additionally, all subjects must meet the study inclusion and exclusion criteria listed below.

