11	Peripheral (outside central 6mm), non-progressive, non-infectious ulcer	Notify sponsor as soon as possible, within 5 working days ; IRB reporting as per requirements
12	Symptomatic corneal infiltrative event	
13	Superior epithelial arcuate lesions (SEALs) involving epithelial split	
14	Corneal staining $\geq$ dense coalescent staining up to 2mm in diameter (e.g. moderate, ISO 11980 grade 3)	
15	Corneal neovascularization $\geq$ 1.0mm vessel penetration (e.g. $\geq$ ISO 111980 Grade 2), if 2 grade change from baseline	
16	Any temporary loss of $\geq$ 2 lines BSCVA for $\geq$ 2wks	
17	Any sign and/or symptom for which subject is administered therapeutic treatment or which necessitates discontinuation of lens wear for $\geq$ 2 weeks	
10	Other significant event	

Non-significant Adverse Events		
21	Conjunctivitis (bacterial, viral or allergic)	Notify sponsor as soon as possible, within 5 working days ; IRB reporting as per requirements
22	Papillary conjunctivitis if $\geq$ mild scattered papillae/follicles approximately 1mm in diameter (e.g. ISO 11890 Grade 2), if 2 grade change from baseline	
23	Asymptomatic corneal infiltrative events	
24	Any sign and/or symptom for which temporary lens discontinuation for > 1 day is recommended (if not already classified)	
20	Other sign and/or symptom warranting classification as a non-significant adverse event	

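### The hypothesis of no difference in anterior ocular health has only mean-based difference tests of slit lamp grades behind it, with no margin, confidence limit or by-lens count, so a non-significant result could not support it

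*Combined protocol and SAP*

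**What the plan says.** Section 2 lists "Anterior ocular health" among the secondary variables. Section 2.1 then hypothesises that "there will be no difference in performance between the Orion Test lens and the Gemini Control lens for any of the secondary variables".

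Section 10.2 names the between-lens method for slit lamp findings: "Paired t-test will be used to compare slit lamp biomicroscopy, lens fit and subjective scores between study lens types". Comparisons between visits use repeated-measures ANOVA or a paired analysis. "The critical alpha level for statistical significance will be set at" p ≤ 0.05, with an unspecified multiplicity adjustment. Summary statistics are promised, with the mean and standard deviation as examples.

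Section 10.1 gives margins for visual acuity (0.1 logMAR) and comfort (−0.75) only. Slit lamp findings have no margin, responder definition, confidence-interval rule or power statement.

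The design is a "double-masked, randomized, bilateral, two-week crossover, dispensing study". On numbers, section 7.1 says: "Up to 70 subjects will be enrolled and dispensed in order for approximately 60 subjects to complete the study".

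The adverse event table in section 8.1 sets thresholds for individual subjects. Code 14 is corneal staining of about ISO grade 3. Codes 15 (neovascularization) and 22 (papillary conjunctivitis) each combine an absolute finding with a further condition, "if 2 grade change from baseline". Section 8.2 requires a form for each event, and for each eye if both are involved. Section 8.3 provides for sponsor review.

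**The concern.** A difference test can reject equality but cannot confirm it. For acuity and comfort the plan at least supplies margins. For ocular health it supplies a hypothesis of no difference and a test whose non-significance says little unless one knows what it could have detected.

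The choice of summary adds to this. The protocol's own markers of a relevant ocular reaction apply subject by subject. If a few wearers react and the others do not, the mean grade moves little, while those few inflate the standard deviation in the denominator of the t statistic.

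At stake is the wording of the ocular health conclusion. Section 3.1 gives the project's aim as matching the comparator's clinical performance, so a statement of no difference could be carried forward with more weight than 60 subjects can give it.

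**Working it through.** **The plan's own figures.** There is no slit lamp calculation to reproduce. The nearest is comfort, the larger of the two sample sizes. Its 53 reproduces as a paired equivalence calculation (two one-sided tests at 0.05, margin 0.75, true difference 0, SD of the difference 1.3 × √2 = 1.84), with power 0.802 at n = 53. It says nothing about ocular health.

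**Inputs**
- n = 60 completers (section 7.1).
- Level 0.05 (section 10.2). Two-sided and unadjusted are assumptions, because neither sidedness nor the adjustment method is stated.
- Reaction size of 2 grades: an assumption, borrowed from the change in codes 15 and 22.
- Reaction rate of 5% on Test and 0% on Control: an assumption.
- SD of the remaining within-subject Test − Control differences (background SD): an assumption, range 0 to 1.0 grade.

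**Step 1: no background noise.** Suppose k of n subjects rise by d grades on Test only and all other differences are zero. The mean difference is kd/n and the sample variance is d²k(n − k)/[n(n − 1)]. The shift d cancels:

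t = √[k(n − 1)/(n − k)]

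- k = 3: √(3 × 59/57) = 1.76
- k = 4: √(4 × 59/56) = 2.05
- critical value on 59 df: 2.00

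At least 4 reactors are therefore needed, whatever the size of the reaction. With k ~ Binomial(60, 0.05), P(k ≥ 4) = 0.353, so the test is non-significant 1 − 0.353 = 65% of the time.

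**Step 2: with background noise.** Simulated differences are N(0, s) + 2 × Bernoulli(0.05), n = 60:

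| Background SD s | Non-significant |
|---|---|
| 0.2 | 73% |
| 0.3 | 76% |
| 0.4 | 79% |
| 0.5 | 82% |
| 1.0 | 90% |

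Any multiplicity adjustment raises these figures.

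**Step 3: a uniform shift is a different matter.** For an average shift of 0.5 SD in all subjects, noncentral-t power at n = 60 is 96.8%. The weakness is specific to reactions in a small subset.

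**Step 4: what counts can and cannot do.**
- Chance of at least one reactor: 1 − 0.95^60 = 95.4%.
- Exact McNemar test with all reactors on Test: 5 give p = 2 × 0.5^5 = 0.0625 and 6 give p = 2 × 0.5^6 = 0.031, so 6 are needed. P(k ≥ 6) = 0.079, so it is non-significant about 92% of the time.
- Exact 95% upper limit for 0/60: 1 − 0.05^(1/60) = 4.9% one-sided, or 1 − 0.025^(1/60) = 6.0% two-sided.
- Exact one-sided 95% upper limits for 1/60 and 3/60: 7.7% and 12.4%.

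A test on counts is therefore weaker than the t-test. What counts add is an estimate with a limit.

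**The case against.** Four objections carry weight.

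**No decision rule is written.** A reader might infer that the plan declares no difference whenever p > 0.05. The documents do not say so: section 2.1 can be read as stating null hypotheses, and the summary statistics in 10.2 are an open list. This stands. What remains is that 10.2 offers no other route to a conclusion on that hypothesis.

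**Reactions are captured individually.** A reader might infer that a harmful reaction would go unseen. It would not. Codes 14, 15 and 22 each require a form and a report to the sponsor within 5 working days, followed by sponsor review. What can be missed is the statistical signal. The remaining gap is that no planned analysis sets these events side by side by lens or bounds their rate.

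**The miss rates depend on assumptions.** A reader might take roughly three in four as a property of this trial. The documents give neither a reaction rate nor a slit lamp SD, and only the 2-grade change has a source in them. The 65% figure is free of the SD and the grade shift but still depends on the 5% and 0% rates.

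**Counting does not restore power.** This is correct, as step 4 shows. The limitation comes from a rare event in 60 subjects, and the t-test is not its cause.

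Two practical cautions also stand. Codes 15 and 22 are composite and cite ISO grades as examples, while the slit lamp CRF uses the sponsor's CVI scale, whose content is not shown. In addition, Pair 2 is dispensed at Visit 2 after only a saline washout, so a finding that persists from Pair 1 could be charged to the wrong lens.

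**Conclusion.** The concern holds in a limited form. The plan hypothesises no difference in anterior ocular health and names only mean-based difference tests for slit lamp grades, so a non-significant result could not support that conclusion.

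The size is illustrative. With 60 completers, 5% affected on Test, none on Control and an unadjusted two-sided 0.05 level, the t-test is non-significant at least about 65% of the time, and 73% to 82% of the time for a 2-grade reaction with background SD 0.2 to 0.5.

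The documents do not support going further, to the claim that the trial would overlook ocular reactions or that it has adopted a rule equating non-significance with equality. For a feasibility study in which ocular health is one of five secondary variables, this is a minor point and a cheap improvement.

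**What to change.** In section 10.2:

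1. Keep the paired t-test on slit lamp grades as descriptive.
2. For each lens, report the number of subjects (worse eye, while on that lens) who meet the slit lamp criteria of codes 14, 15 and 22 in full as section 8.1 writes them. State in advance how those criteria map to the CVI grades on the CRF.
3. Give exact 95% confidence limits for each lens and for the paired difference.
4. Flag findings already present at the end of Pair 1, so that they are not attributed to Pair 2.
5. Replace a conclusion of no difference with wording of the form: x of n on Test, y of n on Control; rates above z% are excluded.

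The cost is a few sentences in 10.2, a mapping of thresholds to the CVI scale, and one table. Slit lamp examination is already scheduled at baseline and at both two-week visits, so no extra visits or subjects are needed. The downside is a more modest claim: even 0 of 60 leaves an upper limit of 4.9% (one-sided) or 6.0% (two-sided).
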